In Aim 3, mediation of the intervention effect on alcohol consumption outcomes by AUD treatment use will be evaluated using the Sobel test utility in Mplus (Path A x Path B). This utility in Mplus is able to evaluate the statistical significance of multiple indirect pathways (e.g., assignment to CBT-TE or control condition → use of AUD treatment assessed at 1- and 3-month follow-up → DDD assessed at 6-month follow-up; assignment to CBT-TE or control condition → use of AUD treatment assessed at 1- and 3- month follow-up → PDA assessed at 6-month follow-up) simultaneously (102-103). The SEM models also allow for comparisons with and without residual direct effects (i.e., effect of intervention condition on drinking outcomes when accounting for the mediating role of AUD treatment engagement) to determine an observed mediation effect is partial or complete. A significant indirect effect and an observed decrement in model fit with the removal of the residual direct effect is indicative of a partially mediated effect, whereas a significant indirect effect and a non-significant change in model fit is indicative of a fully mediated effect. The fit of competing models will be evaluated using model χ^2 , the Comparative Fit Index, and the Root Mean Square Error of Approximation (104-105), with greater changes indicative of poorer fit for the new model (corresponding to the interpretation of a partial mediation).

Secondary analyses: We previously discussed the rationale for secondary analyses focused on select subject characteristics (sex, alcohol-related severity) and treatment considerations (type of care, short-term retention in care). An SEM framework affords the opportunity to conduct secondary analyses on data including (A) moderated mediation analyses of the associations between variables of interest by salient demographic- (e.g., sex) and clinical characteristics (e.g., alcohol-related severity) using multiple groups modeling (106) and/or multiplicative interaction terms (e.g., centered X1, centered X2, and X1 by X2) and (B) latent variable modeling such as latent class analysis to examine subgroups of participants for whom the intervention might be most effective (107). Although the study was not powered specifically to perform these types of sub-group analyses, the sample size will allow us to explore select differences in treatment response as suggested by the literature including comparisons by sex (39-40) and alcohol-related severity (41-42). We will define alcohol-related severity using AUD symptom count, obtained at baseline assessment. We will also explore if the mediating effect of alcohol-related care differs by the type of care received as defined using a 3-group categorization (43), consistent with moderated mediation. In sensitivity analyses, we will repeat the primary analyses using short-term retention in care or “engagement” (45-46) as the measure of alcohol-related care (Aim 1) and as the mediator of alcohol use outcomes (Aim 3).

Missing data: Missing data will be addressed in two ways. First, all models performed in a structural equation modeling framework will use a full information maximum likelihood (FIML) estimator robust to non-normality to account for missing data over time (108). These methods yield unbiased estimates and appropriate standard errors without sacrificing cases (thus maximizing statistical power) when data are missing completely at random or predicted by other variables in a given model but independent of the values of the outcome itself (i.e., missing at random). Statistical comparisons on baseline data (e.g., treatment condition, participant sex, alcohol-related severity) will be made between cases retained and those lost at follow-up to determine differential attrition and which covariates require inclusion in the models to meet the missing at random assumption. Mplus has a variety of FIML estimators for use with different outcome distributions and model specifications. Second, following much of the literature examining RCTs, we will apply intention-to-treat principles to data missing at follow-up (109). Specifically, we will ascribe undesirable values to all missing data points (e.g., assume no treatment use has occurred). Estimates from each method for handling missing data are valuable, as the FIML approach will provide a reasonable estimate of the true intervention effect whereas the intention-to-treat approach will provide lower bounds of the efficacy of the intervention.

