ClinicalTrials.gov Cover Page – Statistical Analysis Plan

Title: Talk Therapy by Phone to Promote Treatment for Alcohol Problems

NCT number: NCT03758274

Date: July 2, 2018

Statistical Design and Power

[figure not shown]
Sample size calculation: Power Analysis: Our estimates of statistical power and required sample size were informed by the prior study by Stecker and colleagues (8). In this study, the control group rate of treatment use was 12%, and the treatment group rate was 31%, representing a 2.58 times increase. Given that this study was the first test of the intervention in a sample with elevated alcohol use, we chose a more conservative effect size of a 2.0 times increase in treatment use to account for the potential uncertainty in the generalized effect size and to buffer against the potential for regression to the mean across conditions. Using this effect size and base rate of treatment use, a sample of 450 participants (~225 in each condition) would provide power of 0.89 at a two-tailed alpha level of 0.05. This sample size allows for a loss of up to 20% of participants at follow-up while maintaining power at 0.81, and serves as a further buffer against the downward bias associated with intention-to-treat principles. In the table, we have provided power estimates using both these conservative settings (i.e., smaller than expected effects with high attrition) and more likely scenarios. We were further conservative in our approach by utilizing a two-tailed alpha level, as there is little reason to anticipate an iatrogenic effect in the current study. Use of a one-tailed alpha (i.e., testing if treatment use is higher in the intervention condition than in the control rather than simply whether they are different), provides power of 0.80 to find an effect as small as 1.75 times difference, with power of 0.73 retained if 20% attrition were observed.

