The baseline sample size of 450 affords us the ability to detect bivariate associations between treatment use and alcohol consumption outcomes at the 6-month follow-up as small as 0.14 with power of 0.85 (0.15 with power of 0.85 and 10% participant attrition; 0.16 with power of 0.85 and 20% participant attrition). We used MacCallum, Browne, and Cai's (110) method for deriving power estimates for the fit of nested SEMs (111), which, in this case, involves comparing freely estimated models to those without certain paths (i.e., models without residual direct effects of treatment condition on alcohol consumption outcomes, which imply full mediation). Following common cut points for model fit (112), we assumed a RMSEA of 0.05 for the well-fitting model and 0.10 for a poor fitting model. With a sample size of 450 and our variables of interest, we have power of approximately 0.87 to detect significant changes in fit associated with eliminating paths from the model.

Randomization procedures. Baseline assessments are performed by the University of Rochester Medical Center (URMC) based study team. After the baseline assessment, subjects will be randomly assigned with equal allocation to Cognitive Behavioral Therapy for Treatment Engagement (CBT-TE) or the control condition. The randomization plan will be generated by [name], co-I and study statistician, using an established SAS macro. Only [name] will have access to the treatment assignment prior to a subject being randomized, eliminating the possibility of selection bias. The randomization will be implemented via a REDCap module. The randomization plan will also include blocking to ensure that an equal number of subjects have been assigned to the two treatment groups after a certain number of subjects have been enrolled (block size). Only [name] will be aware of the block size used.

Statistical Power assuming a baseline sample of 450 participants, 12% treatment use in the control condition, and two-tailed α level of 0.05

Treatment Use % in the Intervention Condition	Attrition Proportion	Statistical Power
24% (2.00X increase)	10%	0.86
27% (2.25X increase)	10%	0.96
30% (2.50X increase)	10%	0.99
24% (2.00X increase)	20%	0.81
27% (2.25X increase)	20%	0.94
30% (2.50X increase)	20%	0.98

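### Aim 3 tests mediation only with the Sobel test, which is conservative and, near the SAP's minimum detectable effects, less powerful than a percentile bootstrap at the same nominal error

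*SAP*

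**What the plan says.** Aim 3 is listed in the SAP under Primary analyses. It asks whether AUD treatment use at 1 and 3 months mediates the effect of condition on drinks per drinking day and percent days abstinent at 6 months. The indirect effect "will be evaluated using the Sobel test utility in Mplus (Path A x Path B". A finding of either partial or full mediation first requires that this indirect effect be significant, so the Sobel result gates both conclusions.

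The power section of the SAP sizes the trial on Aim 1: "a sample of 450 participants (~225 in each condition) would provide power of 0.89 at a two-tailed alpha level of 0.05". For Path B it says that the sample can "detect bivariate associations between treatment use and alcohol consumption outcomes at the 6-month follow-up as small as 0.14 with power of 0.85", and with higher loss "0.16 with power of 0.85 and 20% participant attrition". It also gives a power of about 0.87 for nested-model fit comparisons. It gives no power for the indirect effect itself.

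No bootstrap, Monte Carlo or other interval for the product appears in the SAP. The estimator robust to non-normality, in the Missing data section, deals with non-normal outcomes and missing values. It does not deal with the sampling distribution of Path A x Path B.

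**The concern.** A product of two normal estimates is itself skewed and heavy-tailed unless at least one path is large relative to its standard error. Referring it to a normal distribution makes the test conservative. The Sobel statistic is also always smaller than either of its component z statistics, so adequate power for Path A and adequate power for Path B do not together give adequate power for Path A x Path B.

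The risk is a false negative on the trial's causal-pathway question: whether bringing people into care is how the intervention changes drinking. If the interval were changed only after a null Sobel result, the change would look data-driven.

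**Working it through.** **Inputs from the SAP.** N = 450 allocated 1:1, so n = 225 per arm; two-sided alpha 0.05. The prior study is cited for the base rate ("the control group rate of treatment use was 12" per cent), and "we chose a more conservative effect size of a 2.0 times increase in treatment use" gives 24% in the intervention arm. Path B is r = 0.14 at N = 450 and r = 0.16 at 20% attrition (N = 360). The mediator is binary (Key measures).

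**Reproducing the SAP's figures.**

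- Path A, two proportions with continuity correction. Null SE = √(2 × 0.18 × 0.82 / 225) = 0.0362. Alternative SE = √((0.12 × 0.88 + 0.24 × 0.76) / 225) = 0.0358. Power = Φ[(0.12 − 1/225 − 1.96 × 0.0362) / 0.0358] = Φ(1.25) = 0.89, as stated. The same formula gives 0.86 at 10% attrition and 0.81 at 20%, also as stated.
- Path B, Fisher z. zB = atanh(0.14) × √447 = 2.98, and power = Φ(2.98 − 1.96) = 0.85, as stated.

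**Rough Sobel calculation.** Without continuity correction, zA = 0.12 / 0.0358 = 3.35. Then

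z(Sobel) = zA·zB / √(zA² + zB²) = (3.35 × 2.98) / √(3.35² + 2.98²) = 2.23,

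so power ≈ Φ(2.23 − 1.96) = 0.61. Requiring both paths to be significant gives about 0.918 × 0.846 = 0.78. This already shows the loss; simulation gives the more exact values.

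**Simulation.** Binary mediator at 12% v 24%, normal outcome, no direct effect, Path B adjusted for condition, 1,500 to 5,000 trials per setting. The bootstrap used about 600 resamples. Ranges show the spread across runs. The right-hand column is the percentile bootstrap, the Monte Carlo product interval, or both; where both were run they agree to within about 1 point.

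| Setting | Sobel | Percentile bootstrap / Monte Carlo interval |
|---|---|---|
| N = 450, r = 0.14, no baseline covariate | 0.57–0.60 | 0.75–0.77 |
| N = 360 (20% attrition), r = 0.16 | 0.52 | 0.70–0.73 |
| N = 450, r = 0.14, baseline drinking in model, assumed correlation 0.5 | 0.70–0.71 | 0.84–0.85 |
| Same, assumed correlation 0.7 | 0.81–0.82 | 0.90 |
| N = 450, r = 0.20 | 0.82–0.84 | 0.90–0.91 |
| N = 450, r = 0.30 | 0.89–0.91 | 0.92–0.93 |
| N = 450, 12% v 31%, r = 0.14 | 0.75–0.77 | 0.83–0.84 |

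A logit Path A changes the first Sobel figure little (0.57–0.59).

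**Error rate with Path B null.** Sobel rejects in about 1.7% of trials (1.2–1.9% across runs). The percentile and Monte Carlo intervals reject in about 4–5%. A simple check is that the joint test must reject on both paths, so its rate should be near 0.92 × 0.05 = 0.046; shorter runs scatter around this, up to 0.06. The bias-corrected bootstrap has higher power (0.82–0.83 in the first setting) but rejects 6.4–7.2% when one path is null, so part of its gain comes from excess error.

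**The case against.** The strongest reply concerns size. The value r = 0.14 is described as the smallest association that the sample can detect ("as small as 0.14 with power of 0.85"). It was set to sit at 0.85 power and is not a forecast. The 2.0-fold increase is itself called conservative. A reader might infer that 0.58 is the power to be expected for Aim 3; the documents do not support that, because they state no expected Path B. At r = 0.30 the gap is only 1 to 3 points. This objection stands, and the figures must be read as the lower edge of the range.

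It also stands that the SAP's Preliminary analyses paragraph puts baseline drinking in all models. This raises the z for Path B and narrows the gap to about 8–14 points over the assumed correlations. The documents give no baseline-to-6-month correlation, so that range is an assumption.

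A third reply is that the SAP says the study was powered on Aim 1. That explains why there is no power figure for Aim 3. It is not a reason to choose the weaker test for an aim listed as primary.

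A reader might also infer that the SAP claims 0.85 power for mediation, or that Sobel could produce false claims of mediation. Neither follows. The 0.85 is for the bivariate association, and the Sobel error runs in the safe direction. Aims 1 and 2 do not use the test and are unaffected.

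**Conclusion.** The point holds as an avoidable loss of power in a primary aim. It is not a validity error. At the planned Path A, the minimum detectable Path B and N = 450, Sobel has about 0.58 power against about 0.76, a loss of about 18 points. At 20% attrition with r = 0.16 it is about 0.52 against 0.71. With baseline drinking in the model, or with larger effects, the difference shrinks but Sobel stays lower in every non-null setting examined.

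The direction is secure. The absolute values are less so: they rest on a single binary mediator, a normal outcome, no direct effect and, except where stated, no covariates. Skewed drinking outcomes, or separate 1- and 3-month mediators, would change them.

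**What to change.** In the Aim 3 paragraph of the SAP, replace the Sobel test with a percentile bootstrap 95% confidence interval (for example 5,000 resamples) for each indirect effect, one for drinks per drinking day and one for percent days abstinent. Declare mediation when the interval excludes zero, and use that result in the partial-versus-full decision. Name the percentile type explicitly, because the bias-corrected version is mildly liberal. Report Sobel as a supplement at most. Make the change before the outcome data are analysed.

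The cost is SAP wording and computing time, with no added participants, visits or data. The bootstrap may need full-information maximum likelihood without the robust standard errors for this step only. If so, state it as an exception to the estimator commitment in the Missing data section.
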